2.2 SECONDARY ENDPOINTS

Secondary Efficacy endpoints will be:

(1) The extent of reduction in the WOMAC pain score, relative to baseline, provided by once daily, one-hour application of Vehicle (CGS-200-0), CGS-200-1, and CGS-200-5 at the following assessment times:

Baseline: \leq 30 minutes prior to first daily application Day 5 24 hrs (+/- 3) after last of the 4 daily applications Day 19 15 days (+/- 3) after last of the 4 daily applications Day 64 60 days (+/- 3) after the last of 4 daily applications Day 94 90 days (+/- 3) after the last of 4 daily applications

(2) Day 5, 19, 35, 64, and 94 WOMAC scores on the stiffness and function subscales as well as total WOMAC score (including the WOMAC pain score).

Secondary Safety endpoints will be:

- (1) The distribution by study arms of specific AEs (i.e.: local application site reactions), and other AEs (inclusive of findings for hematology, serum chemistry and urinalysis).
- (2) Evaluate the amount of concomitant pain medications used overtime

Tolerability endpoints (which are secondary in nature) will be:

- (1) The application of study drug does not produce burning-stinging pain ("BSP") at the application site to a degree that is not acceptable to the subject. BSP at the application site, this will be assessed using a 0 10 NRS scale without guideposts. "Acceptability" of BSP will be queried per subject at the end of each application period.
- (2) The application of the study drug does not produce pruritus during application or in the 24 hrs post-application to a degree that is not acceptable to the subject or, if bothersome to the subject, cannot be managed by application of ice or a cold pack or compress.

3.0 STUDY DESIGN

3.1 OVERALL STUDY DESIGN

This is a multi-center, randomized, double-blind clinical trial to examine the comparative effects on OAKP of CGS-200-1 (1% Capsaicin content) (N=40), CGS-200-5 (5% Capsaicin content) (N=40), and CGS-200 Vehicle (no Capsaicin) (N=40) in subjects with OA of the knees according to the 1986 ACR criteria. Assigned doses will be applied at the clinic for 60 minutes on each of four consecutive days.

Subjects will be randomized to one of the three Arms in this study: CGS-200-1 or CGS-200-5 or CGS-200-0 (Vehicle). All subjects will receive 4 consecutive days of treatment and will then be followed up until the Day 94 visit.

Subjects will receive the study arm appropriate treatment as a topical application over the frontal aspect of the knee(s) once daily on four consecutive days. The applications will be at the clinic but by the subject wearing gloves under supervision of clinic personnel. The application will be left in place for 60 minutes and then washed off at the clinic by clinic personnel. The amount of Investigational Drug Product to be applied is estimated to be approximately 0.13 mL based on experience in prior studies. Even though both knee(s) will receive application of study test materials, with regard to reduction in WOMAC pain and VAS pain score associated with study treatments, only one knee will be indicated as the "Study Knee". This will be the knee with the highest WOMAC pain score at baseline. If both knees have equal WOMAC pain scores at baseline, then the right knee will be considered the "Study Knee" with regard to WOMAC pain and VAS pain score reduction.

Data will be collected from Day 1 through Day 5 and then again on Days 19, 35, 64, and 94 for efficacy, tolerability, and safety measures. The Investigators, all site staff and Clinical Research Organization (CRO) personnel (except the Medical Monitor providing safety oversight) directly involved in the study will remain blinded to the treatment assignment throughout the trial.

3.2 DOSE LIMITING TOXICITY

AEs and SAEs will be assessed according to the Rheumatology Common Toxicity Criteria (RCTC) v2.0^[8] (Appendix B).

Dose limiting toxicity (DLT) stopping rules for the study drug are based mainly on Grade 2 events related to the study drug, with the following exceptions:

- 1. Cutaneous CGS-200-1 (Capsaicin 1% Topical Liquid) and CGS-200-5 (Capsaicin 5% Topical Liquid) have the potential for being associated with Grade 2 administration site reactions such as erythema, pain and edema, and the DLT threshold has been set at Grade 3.
- 2. The cut-point of Grade 3 to define a DLT and stop further administration of study drug was selected for the safety of subjects since the RCTC only require permanent discontinuation of drugs that attain a Grade 4.

A DLT will be defined as any toxicity occurring within 14 days of treatment with the investigational product, and meeting the following criteria:

- > Grade 3 AE including:
 - Allergic / Immunologic: immune reactions, rhinitis;
 - Cardiac: hypertension, hypotension;
 - Dermatologic: reaction at site of study drug administration;
 - Neuropsychiatric: inability to concentrate, insomnia (in absence of pain), peripheral sensory neuropathy.
- Any other ≥ Grade 2 AE (excluding AEs captured above and pre-existing OArelated conditions).

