6.7 RECOMMENDATIONS FOR MANAGEMENT OF POTENTIAL TOXICITIES

6.7.1 Allergic Reaction, Burning, or Pruritus

In the case of any life-threatening event occurring during the treatment, the study drug must be immediately and permanently discontinued. While corticosteroids are strongly discouraged, they may be used if they are necessary for the safety of the subject.

• Rash/pruritus/urticaria

- If subject develops rash, pruritus, or urticaria, interrupt treatment if it is ongoing and promptly assess subject for any other associated signs/symptoms (e.g., hypotension, fever, respiratory distress).
 - Consider treating with H2 receptor antagonists as clinically indicated.
 If rash / pruritus / urticaria is isolated and resolves either spontaneously or with intervention, treatment with the study drug may be restarted.

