6.9.2 General Criteria for Stopping Study Drug

The study drug will be permanently discontinued for any subject who meets a DLT criterion as outlined in Section 3.2.

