6.9.3 Stopping Criteria

Any \geq Grade 3 event considered related to the study drug and occurring during administration of the study drug will result in its permanent discontinuation for that subject. The Medical Monitor should be notified immediately and the subject should be followed for safety as clinically indicated until the toxicity resolves and in the opinion of the investigator, no further follow-up regarding the toxicity is needed.

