7.2.5 Adverse Event Summaries

All AEs (serious and non-serious) occurring after study drug administration and before the end of study, regardless of relationship to study drug, will be included and classified by SOC and PT using MedDRA.

For TEAEs, the following will be summarized and presented for the SAF set:

- i. An overall summary of TEAEs, which includes:
 - a. the number and percentage of subjects experiencing a TEAE
 - b. the number and percentage of subjects experiencing a TEAE by strongest relationship to study medication
 - c. the number and percentage of subjects experiencing a TEAE by highest RCTC toxicity grade
 - d. the number and percentage of subjects experiencing a DLT
 - e. the number and percentage of subjects experiencing a treatment emergent SAE (TESAE)
 - f. the number and percentage of subjects experiencing a TEAE leading to death
 - g. the number and percentage of subjects experiencing a TEAE leading to study withdrawal
 - ii. the number and percentage of subjects experiencing a TEAE by SOC and PT.
 - iii. the number and percentage of subjects experiencing a TEAE by SOC, PT and the strongest
-

relationship to study medication

- iv. the number and percentage of subjects experiencing a TEAE by SOC, PT and the highest RCTC toxicity grade
- v. the number and percentage of subjects experiencing a DLT by SOC and PT
- vi. the number and percentage of subjects experiencing a TESAE by SOC and PT
- vii. the number and percentage of subjects experiencing a TEAE leading to study withdrawal by SOC and PT

In the overall summary of TEAEs table (i), besides tabulating the number and percentage of subjects, the total number of TEAE episodes will also be provided. If a subject has repeated episodes of a particular TEAE, all episodes will be counted in the summary table.

In the remaining summary tables, the incidence of TEAEs will be calculated by dividing the number of subjects who have experienced the event by the total number of subjects in the SAF set. Thus, the incidence of TEAEs is shown in terms of the total number of subjects and not in terms of the total number of episodes. If a subject has repeated episodes of a particular TEAE, only the most severe episode, or the episode with the strongest causal relationship to study drug, will be counted in the summary tables.

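### Protocol 3.2 is inconsistent on whether a dose-limiting toxicity must be drug-related and at what grade, and the SAP tabulates DLTs without defining them

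*Protocol*

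**What the plan says.** **Protocol 3.2** describes a DLT in three ways.

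- The introduction says that the "stopping rules for the study drug are based mainly on Grade 2 events related to the study drug", with exceptions.
- The second exception says: "The cut-point of Grade 3 to define a DLT and stop further administration of study drug was selected for the safety of subjects".
- The operative definition reads: "A DLT will be defined as any toxicity occurring within 14 days of treatment with the investigational product, and meeting the following criteria". Two criteria follow. The first is a Grade 3 tier for named categories: allergic/immunologic, cardiac, reaction at the application site, and some neuropsychiatric events. The second is "Any other ≥ Grade 2 AE (excluding AEs captured above and pre-existing OArelated conditions".

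**Protocol 8.1.1** defines an adverse event by its timing relative to the drug and states that it need not be caused by it.

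**Protocol 6.9.2**: "The study drug will be permanently discontinued for any subject who meets a DLT criterion as outlined in Section 3.2". Section 6.10 also lists a DLT as the reason for removal from treatment.

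**Protocol 6.9.3** covers events of Grade 3 or higher: any such "event considered related to the study drug and occurring during administration of the study drug will result in its permanent discontinuation" for that subject.

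**SAP 7.2.5** plans an overall DLT count and "the number and percentage of subjects experiencing a DLT by SOC and PT", and the AE listing carries a DLT flag. SAP 7.2 defines treatment-emergent AEs, severity, relationship and SAEs, but gives no DLT criteria. SAP 3.2.4 names a DLT as a reason for removal from treatment, also without criteria.

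**The concern.** A DLT has two uses in this trial: it stops a subject's dosing, and it is a reported safety result. Both need one definition. The introduction to 3.2 requires a related event. The operative text does not, and the AE definition in 8.1.1 cannot supply the missing condition. The same section also gives both Grade 2 and Grade 3 as the threshold without fully explaining how they fit.

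A site that applies the operative text would permanently stop a subject for a Grade 2 event that the investigator judges unrelated. A site that applies the introduction would not. The SAP percentage would then mix two rules, or rest on whichever one the programmer chose.

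**Working it through.** **Nothing to reproduce.** The documents state no expected DLT rate and no DLT threshold for the study. The only design calculation (SAP 9, power for WOMAC pain) does not bear on this point. What follows is a comparison of texts, then an illustration of size.

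**Step 1: the texts side by side.**

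| Source | Grade | Related to drug? | Time |
|---|---|---|---|
| 3.2, introduction | mainly Grade 2 | yes | not stated |
| 3.2, second exception | Grade 3 | not stated | not stated |
| 3.2, operative, named categories | Grade 3 tier | not stated | within 14 days |
| 3.2, operative, all other AEs | Grade 2 or higher | not stated | within 14 days |
| 6.9.2 and 6.10 | as 3.2 | as 3.2 | as 3.2 |
| 6.9.3 | Grade 3 or higher | yes | during administration |
| SAP 7.2.5 | not stated | not stated | not stated |

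The last operative row has two carve-outs: events already captured in the named categories, and pre-existing conditions related to osteoarthritis. Neither concerns causality. An unrelated Grade 2 event outside the named categories is thus a DLT under the operative text and is not one under the introduction. The exact inequality sign on the Grade 3 tier may have been altered in text extraction, and nothing here depends on it.

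**Step 2: the window.** The 14 days are not anchored. Counted from the first application (Day 1) they run to 1 + 14 = Day 15. Counted from the last (Day 4) they run to 4 + 14 = Day 18.

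**Step 3: which events can change dosing.** Applications are on Days 1 to 4 only. An event before the fourth application can stop dosing. A later event in the window can change only the DLT count.

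**Step 4: illustration of the count.** Inputs: n = 40 per arm (SAP 9); q = the chance that a subject has an unrelated, qualifying event in the window. The documents do not give q; 5% to 15% is an assumption.

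- Extra subjects per arm, if no related DLTs occur = 40 × q.
- Chance of at least one in an arm = 1 − (1 − q)^40.
- Reported rate with a related DLT rate r = r + q(1 − r), shown for r = 5% (also assumed).

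| q | 40 × q | At least one | Reported rate if r = 5% |
|---|---|---|---|
| 5% | 2 | 87% | 0.05 + 0.05 × 0.95 = 9.75% |
| 10% | 4 | 98.5% | 0.05 + 0.10 × 0.95 = 14.5% |
| 15% | 6 | above 99% | 0.05 + 0.15 × 0.95 = 19.25% |

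Under a related-only reading the last column would be 5% throughout.

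**Step 5: illustration for dosing.** If events were spread evenly over 14 days from the first application (assumption), 3/14 would precede the fourth application: 2 × 3/14 = 0.4 to 6 × 3/14 = 1.3 subjects per arm.

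**The case against.** The best defence of the text is that relatedness is implied. The sentence opening 3.2 mentions it, and the definition speaks of a toxicity rather than an event. That reading is possible. But the introduction says mainly, the criterion itself says AE, and 8.1.1 does not tie AEs to the drug. The defence shows an ambiguity and does not resolve it.

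Several stronger readings are tempting, and the documents do not support them.

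- **That 6.9.3 contradicts 6.9.2.** A reader might infer that 6.9.3 limits stopping to related events of Grade 3 or higher. It does not say only. It is a sufficient condition, and a site can obey both sections by stopping when either is met. What stands is that the protocol does not say how the two fit together.
- **That the restart provisions conflict with 3.2.** Section 6.7.1 says that after isolated rash, pruritus or urticaria "treatment with the study drug may be restarted", and 5.1.4 allows a restart to be considered after a Grade 2 allergic reaction. Allergic and application-site reactions fall largely in the Grade 3 tier of 3.2, where a restart after Grade 2 is consistent. Only a Grade 2 rash outside those categories would clash. These sections need checking, but they are not the main evidence.
- **That accepting Grade 2 laboratory findings in the primary safety endpoint contradicts the DLT rule.** An endpoint and a stopping rule may use different thresholds, and the Day 5 samples come after the last application.
- **That unrelated events would hide a dose difference.** With a common background q, the difference between arms is multiplied by 1 − q, that is 0.85 to 0.95 at the assumed rates. SAP 7 plans no hypothesis tests on safety.

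It is also fair to say that the AE listing in SAP 7.2.5 carries grade, relationship, onset day and the DLT flag, so much of the split could be rebuilt by hand. That lowers the cost of the defect. It does not tell sites which subjects to stop, or the programmer which events to flag.

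**Conclusion.** The point holds as an internal inconsistency in Protocol 3.2, on relatedness and on grade, carried into discontinuation by 6.9.2 and 6.10 and into reporting by the SAP. Applied literally, the operative definition stops and counts subjects on a basis that its own introduction does not state.

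Its size cannot be estimated from the documents. The 2 to 6 extra DLTs per 40-subject arm rest wholly on the assumed 5-15% rate and concern the reported count. A reader might take them as subjects lost from dosing, but only events before the fourth application can have that effect: about 0.4 to 1.3 subjects per arm under the further assumption of even spread. Stopped subjects are followed through Day 35 (6.10), so the planned follow-up still covers the primary time point. DLT is not itself an endpoint, and the documents set no study-level DLT threshold. This should be corrected, but it does not threaten the primary efficacy analysis.

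**What to change.** 1. Reconcile Protocol 3.2, 6.9.2 and 6.9.3 into one DLT definition that states grade, relatedness and when the 14-day window starts, and say how 6.9.2 and 6.9.3 work together. Then check 5.1.4 and 6.7.1 against the result. Which clinical rule applies is for the sponsor to decide; this review takes no position.
2. In SAP 7.2, refer to that single definition.
3. In SAP 7.2.5, present DLTs split by Related/Not Related and by grade, so that the result can be read under either wording.

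The cost is a clarifying amendment and one extra split in a planned safety table. Grade and relatedness are already recorded for every AE, so no new data are needed.

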4.0 SELECTION AND WITHDRAWAL OF SUBJECTS

4.1 INCLUSION/ EXCLUSION CRITERIA:

Subjects entering the study must meet all inclusion and exclusion criteria.

4.1.1 Inclusion Criteria:

The subject must meet all of the following:

- 1. Able to comprehend the informed consent form (ICF) and provide Informed Consent, and capable of complying with all study procedures;
- 2. Male or female, 35 years of age to 75 years;
- 3. OA of the at least one knee according to 1986 ACR Classification Criteria;
- 4. OA of at least one knee must be confirmed by tibiofemoral joint radiographs obtained within the past 6 months;
- 5. RF negative and ESR <40 mm/hr;
- 6. Chronic knee pain in at least one knee for > 3 months;
- 7. WOMAC pain score of \geq 250 (using VAS WOMAC format) at screening, and at baseline, in at least one knee;
- 8. Knee pain score of \geq 5 on the NRS pain scale at screening, and at baseline, in at least one knee;
- 9. Knee pain is not potentially due to acute trauma unrelated to OA (no acute traumatic knee injury in medical history);
- 10. No burning-stinging pain, unrelated to subject's knee pain, at intended site of application;
- 11. Knee pain must be greater than pain in any other part of subject's body;
- 12. ACR global functional status I, II, or III (excluding IV);

13. If female, subject must be past childbearing age or otherwise must test negative for pregnancy. Males and females must agree to use effective birth control for at least 30 days after last dose of study drug.

4.1.2 Exclusion Criteria:

The subject must not have any of the following:

- 1. Spontaneously improving or rapidly deteriorating OA of the knee;
- 2. Rheumatoid or psoriatic arthritis, or a form of arthritis (e.g. gout, pseudogout), Paget's disease of bone, or any other disease affecting the joints that are inconsistent with a diagnosis of idiopathic OA;
- 3. Use of topical, oral, or injectable steroids for 1 month prior to screening, or intraarticular-visco-supplementation within 3 months prior to screening;
- 4. Used any capsaicin-containing product on or in the vicinity of the knee within 4 weeks prior to screening;
- 5. Used topically applied products (including emollients or moisturizers) on or in the vicinity of the knees or shaved the knees within 2 days prior to the first application of study drug; or an open wound near the knee; cutaneous erythema or edema; any inflammatory skin lesions such as eczema or psoriasis; cutaneous infections; or any other compromise of the skin;
- 6. A history of sensitivity to topical substances inclusive of OTC topical analgesics;
- 7. Significant cardiovascular, renal, or other diseases or conditions, or laboratory or other test abnormalities that, in the opinion of the Investigator, would contraindicate participation in the trial;
- 8. Labile or poorly controlled hypertension;
- 9. A psychiatric disorder or significant anxiety or depression that could interfere with the subject's compliance with study procedures or completion of the study;

- 10. Requires daytime use of medications or substances (alcohol, benzodiazepines, barbiturates, muscle relaxants, tranquilizers, hypnotics) that could diminish their cognitive ability to comply with study procedures;
- 11. A history of drug or alcohol abuse within one year prior to screening;
- 12. Requires or anticipates any surgical procedure within 3 months prior to screening, has had surgery on the affected joint within 6 months prior to screening, has a prosthesis in either knee, or would require surgery while participating in the trial;
- 13. Pregnant or nursing;
- 14. Treated with an investigational drug, device or therapy within 30 days prior to screening.
- 15. Body mass index greater than 45 kg/m²
- 16. Skin on or near knee is broken or damaged or if there is an open wound on or near the knee.

4.2 REPLACEMENT OF SUBJECTS

Subjects that do not receive 4 complete consecutive daily doses and/or drop out before completing the Day 35 visit may be replaced if the reason for dropping out is other than lack of drug product tolerability. A dose will be considered complete when at least 80% has been delivered on any study drug administration day; dosing will be considered complete overall when a total of at least 80%, in the aggregate, has been delivered across all study treatment days. Subjects that drop out or who cannot be followed up from after the Day 5 visit until the Day 35 visit may be replaced. Up to 10 subjects per arm may be replaced.

5.0 STUDY TREATMENT

5.1 CGS-200-1, CGS-200-5, AND CGS-200-0 (VEHICLE)

5.1.1 Formulation

CGS-200-1 and CGS-200-5 are topical analgesic liquids intended for application to intact, non-irritated skin in adults with musculoskeletal pain, including pain of OA of the hands, wrists, elbows, or knees for the relief of pain, reduction of stiffness, and increased functional activity.

CGS-200-1 is a multi-component formulation in which the active ingredient for the intended therapeutic effect is capsaicin at a level of 1% for this study.

CGS-200-5 is a multi-component formulation in which the active ingredient for the intended therapeutic effect is capsaicin at a level of up to 5% for this study.

CGS-200-0 (Vehicle) contains all of the ingredients in CGS-200-1 and CGS-200-5 except for capsaicin.

The composition of study test materials is provided in the table below.

Ingredient	CGS-200-5 % w/w	CGS-200-1 % w/w	CGS-200-0 Vehicle % w/w
Capsaicin	5	1	0
Dehydrated Alcohol	20	20	22.5
Polysorbate 80	10	8	7
Diethylene Glycol Methyl Ether	10	10	10
Propylene Glycol	10	10	10
Na Hyaluronate (~1,000K Daltons)	0.15	0.16	0.17
Na Hyaluronate SLMW (~20K Daltons)	0.30	0.32	0.33
Distilled Water	44.55	50.52	50
Totals	100.00	100.00	100.00

CGS-200-1, CGS-200-5, and CGS-200-0 Vehicle will be stored at room temperature (15 - 30°C) in a limited access location, protected from excessive light and heat. Storage conditions must also comply with the site's institutional procedures and all applicable regulatory requirements.

5.1.2 Packaging, Labeling and Storage

The vial label will contain the following information at a minimum:

- Blinded code number
- Volume (single dose vial; fill volume is up to 0.35mL)
- Storage instructions
- Manufacture Date
- Investigational drug statement
- Name of manufacturer
- Name of sponsor

Study drug inventory/accountability forms will be monitored during the study and reconciled by the study monitor at the end of the study. All used and unused investigational study drug must be accounted for on a study drug accountability form provided to the investigator by the site monitor.

